In the equation, the basal rate from midnight to 3 am on a future day, is denoted with a superscript $N+1$, is calculated from the value used on the current day, denoted by superscript N . Recommendations to increase or decrease the basal rate are based not just on whether the CGM glucose value is below target, but also on what the rate of change of glucose is at that time. Thus, a 3 AM CGM value that is consistently at target but decreasing may result in a recommendation to decrease the midnight to 3 AM basal rate, and a value is above target but approaching target at a desired rate may leave the basal rate un-changed, the desired rate being set by parameter T_I . Changes are not made from day-to-day; rather, the value is updated each day but needs to pass a threshold set by the user (0.05 U/hr in this simulation). Thus, a value slightly above target range on one day, and slightly below target on a subsequent day,

has no net effect, with a change only occurring following an interval where the values are consistently above or below target. In the simulation study, the pump basal rates were initially set to be higher than needed, leading to a 3 AM glucose value of 50 mg/dL on the first observation (simulating a night following a high level of activity during the day). For the values of K_P and T_I chosen, the first recommended change requires a repeat occurrence at 50 mg/dL, and a total 6

[figure not shown]

Figure 1. Simulated pump adaptation showing changes in 3 am glucose over 28 days of adaptive pump therapy.

changes are required to decrease the basal rate from the initial 0.5 U/hr to 0.2 U/hr. Different values of K_P and T_I lead to more rapid or slower adaptation. As well, the target range can be decreased, but will require additional pump adjustments that the physician or patients may find unnecessary.

Figure 2.

$$BASAL_{0-3}^{N+1} = BASAL_{0-3}^N + K_P(G_{3am} - \text{target})/T_I + K_P \frac{dG_{3am}}{dt}$$

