days will be initially defined as any day where the activity is greater than one standard deviation above the mean. This definition, however, may need to be adjusted on a subject specific basis as it may vary due to physical fitness. Nadir glucose on increased activity days will be inputted into an adaptive basal algorithm. The algorithm is initialized with the subject's baseline insulin rate settings. Once the algorithm detects a need to modify the basal rate based on activity level, then an alternate basal profile will be recommended by the study physicians if deemed appropriate. The change will be made by the parent during one of the scheduled weekly phone calls or any other time of the week if needed. A study team member will walk the parent through the required steps to change insulin pump settings and confirm by verbal read back, screenshot or download that the pump settings are correct. Any changes to insulin pump therapy will be communicated to the subject's primary diabetes team via a note entered into the patient's BCH medical record.

Subject-Study Team communication: All subjects/families will be asked to contact the study team and perform a data download on a weekly basis. Families will be asked if they were compliant with CGM and activity monitor, if they had issues with blood glucose levels and if there were any intercurrent illnesses. Additionally, participants should contact a study team member if they experience any technical difficulties with their CGM or activity monitor, if they experience any nocturnal hypoglycemia (confirmed by home glucometer) or if they have concerns regarding a high activity day. Study team members will review daily activity data and call subject's families if an insulin dose change is recommended. A study team member will be available on page 24 hours a day.

Safety Monitoring: If CGM review reveals significant and recurrent hyperglycemia or activity-unrelated hypoglycemia, the subject's diabetes team will be alerted so that they may decide if changes to the subject's baseline insulin regimen are required. The study team may enact nighttime basal insulin dosing changes if significant nocturnal hyperglycemia is encountered while simultaneously alerting the patient's primary diabetes providers of these changes and giving them the option to change or refuse the recommendation.

d. **Definition of Primary and Secondary Outcomes/Endpoints**

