Data analysis will begin by calculating the baseline (average and standard deviation) activity level for each subject during the first two to six weeks. High activity days will be defined as any day where the activity is greater than one standard deviation above the mean. Correlations will be performed to assess if there is relationship between daytime activity (8- am to 9 pm) and nighttime nadir blood glucose level (continuous). Nadir glucose will also be categorized as hypo- or no-hypo (binary), with a binary logistic regression model used to assess the significance of daytime activity, insulin dosing, and carbohydrate intake, as independent factors increasing the risk of hypoglycemia. Analysis will proceed with generalized estimating equations (not powered but in preparation of the larger study to be conducted). Characteristics of the nighttime glucose profile (nadir glucose, time in target, time below target) will be calculated weekly, with mean and 95% confidence plotted by week. In the event usual-care pump settings are adjusted during the course of the study, the average nighttime glucose values observed for the week following the most recent adjustment will be compared to average values obtained during the final week (assures improvements are due to the availability of the FitBit data rather than the CGM data). Chi2 analysis will be used to assess differences in the incidence of hypoglycemia. Statistical analyses will be performed both as intention to treat and per protocol. The intention to treat analysis will include all data; per protocol analysis will exclude cases in which the subject does not comply with recommendations of the study team or does not complete all 12 weeks of the study. The algorithm will be considered feasible if all data can be assembled, and recommendations deemed reasonable (accepted) in a majority of cases.

Statistical Power and Sample Considerations

This is a feasibility study and therefore is not powered; however, the choice of 10 subjects with any one group is generally considered acceptable for feasibility/pilot-studies and should provide sufficient data to power a larger study.

Study Organization

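### The final-week glucose comparison averages all nights, but the activity-based rate applies only after high-activity days (about 1 night in 7), so it cannot attribute a change to the activity data

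*Combined protocol and SAP*

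**What the plan says.** - **Simulation (Section 3, Preliminary studies).** The algorithm works on the 3 am glucose, and "the value is updated each day but needs to pass a threshold set by the user", set there at 0.05 U/hr. The figure legend reads "Simulated pump adaptation showing changes in 3 am glucose over 28 days of adaptive pump therapy". On timing, "the first recommended change requires a repeat occurrence at 50 mg/dL"; on size, six "changes are required to decrease the basal rate from the initial 0.5 U/hr to 0.2 U/hr".
- **Trial input (Section 4.c, Changes in Pump Therapy Based on Activity).** "Nadir glucose on increased activity days will be inputted into an adaptive basal algorithm". A high-activity day is at first one that lies more than one SD above the child's mean over 14 days of baseline data. The section allows this cut-off to be changed for individual children.
- **When the alternate rate applies (Section 4.a).** It is recommended on increased-activity days, in a window that opens between weeks 3 and 6 and closes between weeks 12 and 16. The target is the overnight nadir on usual-care settings.
- **Analysis (Section 5.a).** If usual-care settings were adjusted during the study, average nighttime glucose in the week after the latest adjustment "will be compared to average values obtained during the final week". The plan adds that this ensures improvement comes from the activity-monitor data and not from CGM. The comparison is not limited to nights after high-activity days.

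The documents do not state how many flagged-day updates are expected or needed.

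**The concern.** The comparison has one stated job: to separate what the activity data achieved from what CGM achieved. The activity-based rate can act only on flagged nights, while the average covers every night of the week. If flagged nights are few, most of the average comes from nights on usual settings. A real benefit would then look small, and a drift on ordinary nights, from whatever cause, could be credited to the activity data.

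There is a second, weaker question. The simulation updated the rate once a day; the trial updates it only on flagged days. A final-week result may therefore describe a rate that is still moving. At stake are the reading of this contrast and any planning figure that might be taken from it.

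**Working it through.** **Plan's own figure.** (0.5 − 0.2) / 0.05 = 6 changes, as stated in Section 3.

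**Share of days flagged.** The documents give no rate, so normally distributed activity and an unchanged cut-off are assumed.
- Mean and SD known: 1 − Φ(1) = 0.159.
- Mean and SD estimated from 14 days: P(t with 13 df > 1/√(1 + 1/14)) = 0.176 on average.
- Sampling error in the 14-day mean and SD gives a 95% range of about 5% to 37% for a single child.

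**Final week.**
- Flagged nights per child: 7 × 0.159 = 1.1 (7 × 0.176 = 1.2 with the 14-day baseline; 7 × 0.05 = 0.35 to 7 × 0.37 = 2.6 across children).
- All 20 children: 140 × 0.159 = about 22 of 140 child-nights.
- Chance that a child has none: 0.841^7 = 0.30 (0.824^7 = 0.26 with the 14-day baseline). At most one: 0.69.

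**Dilution.** Let the alternate rate shift glucose by X on flagged nights and by nothing on others. The weekly average moves by (1.1/7)X = 0.16X, or 0.05X to 0.37X across the per-child range. This takes adaptation as complete and the reference week as free of alternate-rate nights. If the reference week contains some, the difference is smaller still.

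**Number of updates.** Expected flagged days = 0.159 × days in the window:

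| Window | Days | Updates in window | Updates before final week |
|---|---|---|---|
| Weeks 7–12 | 42 | 6.7 | 5.6 |
| Weeks 3–12 (or 7–16) | 70 | 11.1 | 10.0 |
| Weeks 3–16 | 98 | 15.5 | 14.4 |

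**Updates needed.** K_P and T_I are not given, and the plan notes that "Different values of K_P and T_I lead to more rapid or slower adaptation". The rule was therefore re-run without the rate-of-change term. Glucose was taken as linear in the basal rate, the target as 110 to 130 mg/dL, and the first-night step as 0.025 to just under 0.05 U/hr, so that the first change falls on the second observation. Over 72 settings, all six changes took 10 to 30 updates (median 18), and 68 settings finished within 28. The first three changes took 4 to 8.

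**Chance of enough updates before the final week** (binomial, rate 0.159):

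| Updates needed | 6-week window | 10-week window | 14-week window |
|---|---|---|---|
| 4 (three changes, fast) | 83% | 99% | over 99% |
| 8 (three changes, slow) | 18% | 80% | 98% |
| 10 (six changes, fastest) | 4% | 55% | 93% |
| 14 | under 0.1% | 12% | 59% |
| 18 (six changes, median) | 0% | 1% | 19% |

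Letting the flagged rate vary between children widens this. For 18 updates the chances become 1%, 15% and 38%; for 10 they become 17%, 55% and 77%.

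**The case against.** The strongest reply is that this contrast is a minor part of an unpowered pilot. It applies only if usual-care settings were adjusted. Feasibility is judged on whether the data can be assembled and most recommendations are accepted, and neither depends on the contrast. An all-night average is also a legitimate description of what was achieved by study end, and the larger study's endpoint, nighttime hypoglycemia, is not restricted to high-activity nights. The plan has weekly plots and a night-level model as well. All of this stands. It limits the point to the attribution claim, which an all-night average cannot support.

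A reader might go further in three ways that the documents do not support.
- **That adaptation would usually be unfinished.** The simulation began from rates deliberately set too high and aimed at 110–130 mg/dL. The trial starts from usual-care settings and targets the usual-care nadir, so the correction needed is unknown. A half-size correction would usually finish in the 10- and 14-week windows. Nor does the simulation's 28-day length mean that 28 updates are needed, which at 0.159 per day would take 28 / 0.159 / 7 = about 25 weeks.
- **That Section 5.a assumes a settled rate.** It does not say so.
- **That the larger study's power would rest on this contrast.** Section 4.d says only that the larger study will be powered from the pilot's data, and Section 5.a ties that preparation to the GEE.

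The flagged-day share is also soft: activity may not be normal, and the cut-off may be changed by child.

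**Conclusion.** The point holds for attribution. Under normal activity and the initial cut-off, about 1.1 of 7 final-week nights per child could carry the alternate rate, about 30% of children would have none, and an effect X appears as about 0.16X (0.05X to 0.37X per child from baseline sampling error). A change in the all-night average therefore cannot be credited to the activity data, even if adaptation is complete.

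The update-frequency part holds only conditionally. With about 7 to 16 updates per child, adaptation could be incomplete in the final week if the correction is as large as the simulated one. That rests on a re-run with unstated constants filled in by assumption. Both parts concern a comparison made only when usual-care settings changed; the feasibility criterion is untouched. This is a worthwhile, inexpensive improvement to the analysis plan.

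**What to change.** - **Keep** the final-week average as a description, and do not attribute a change in it to the activity data.
- **Add** a within-child contrast limited to high-activity nights: all such nights from the first alternate-rate recommendation onward, against that child's high-activity nights on usual settings. Where available, use only nights after the most recent usual-care adjustment, which preserves the plan's protection against CGM-driven changes.
- **Do not restrict** the later period to nights after the last rate change. The algorithm stops changing the rate once glucose is satisfactory, so that restriction would select on outcome.
- **Fit** the contrast in the planned night-level GEE, with an indicator for alternate rate in use.
- **Report** the number of flagged-day updates per child and how many children had a stable alternate rate at study end.

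The cost is analysis-plan wording; no new data are needed. The contrast uses fewer nights, so its intervals will be wider. A 14-day baseline gives only about 14 × 0.159 = 2.2 flagged nights per child, and some children will have none in one of the periods. Low nadirs on usual settings are also what trigger a recommendation, so some apparent gain from regression to the mean is possible and the estimate should be presented as descriptive.

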The initial 2 weeks of a subject's enrollment in the study will be used to establish his or her baseline activity level and no changes to the insulin regimen will be made based on the activity monitor data. During weeks 3-6 to 12-16, activity data will be reviewed daily and an alternate basal insulin rate will be recommended on days considered to be increased activity days. We will use an adaptive algorithm to help guide suggested nighttime insulin basal rate changes. All recommendations will be reviewed and approved by a study physician prior to implementation. The alternate rate will be derived using the subject's usual care pump settings as an initial starting point from which to make incremental changes in the 3 hour interval leading up to the hypoglycemic event. Target will be the overnight nadir obtained with usual care settings. Residual error (CGM-target) will be used to assess the validity of using the 3 hour window prior to the event to effect lower basal. The patient's primary diabetes team will be informed about the recommended nighttime basal insulin dose change and this will be documented in the patient's medical record in powerchart. The primary diabetes team will not give recommendations regarding nighttime insulin rate dose changes based on activity monitor data; however, they will continue to guide all other aspects of the patient's diabetes management.

b. Patient Selection and Inclusion/Exclusion Criteria

Subjects will be recruited from the outpatient endocrinology clinic based on physician recommendation and approval to approach at Boston Children's Hospital (BCH) as well as through public notice. 20 subjects will be recruited in two different age designations.

Inclusion Criteria:

- Age: 1 to 17 years old
- Type 1 diabetes (as clinically diagnosed by outpatient endocrinologist).
- Treated with insulin pump therapy for greater than or equal 3 months

- Families will need to have access to Wi-Fi and a compatible smartphone in order for the data from the activity monitor and other devices to be transmitted to the research team

Exclusion Criteria:

- Current glucocorticoid use or other medication known to affect insulin action at investigator's discretion.
- Hospitalization within the last month

c. **Description of Study Treatments and Procedures**

RECRUITMENT, SCREENING AND CONSENT:

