Insulin Pump Therapy: Participants will continue to use their own insulin pump and home blood glucose meter. All subjects will continue to receive routine care from their primary diabetes team. We propose to enact insulin dosing changes if we discover significant hyperglycemia and informing the diabetes providers of these changes." All other insulin dose changes unrelated to activity monitor data and energy expenditure estimates will be at the discretion of the primary team. We recognize that initial use of CGM may reveal previously undetected hypo- or hyperglycemia. Subjects and their families should discuss these findings with their primary diabetes team as they would for any other concerning blood glucose levels. If significant nocturnal hyperglycemia is detected, an increase in nighttime insulin basal rate will be recommended by the study team after being reviewed by the study endocrinologist. The dosing changes to address the hyperglycemia will be made by the study team directly in order to prevent delays in correction of the hyperglycemia as can occur if forced to wait for a response from the primary provider. Nevertheless, Tte recommended changes will also be sent as a powerchart message to the subject's primary diabetes care team and they will be given the option to opt out of the recommendation and contact the patient directly to address the discovered hyperglycemia. If the provider responds after the changes have been enacted then we will simply contact the family and ask them to resume their prior settings and discuss with their provider an alternative plan to treat the hyperglycemia.

Changes in Pump Therapy Based on Activity: During the first two to six weeks of the study, a baseline activity level will be established for each subject (average and standard deviation of first 14 days of available data). High activity

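### The activity–nadir correlation pools nights on which high activity triggered a basal reduction, so it is biased toward zero wherever the reductions work

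*Combined protocol and SAP*

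**What the plan says.** Section 4a: once baseline is over, activity is reviewed daily and "an alternate basal insulin rate will be recommended on days considered to be increased activity days". The aim of the change is also stated: "Target will be the overnight nadir obtained with usual care settings". Section 4d gives its direction, a reduction in basal delivery after high-activity days. Section 4c feeds nadirs from high-activity days into the adaptive algorithm, and a study physician must judge any resulting change appropriate.

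Section 4c defines baseline by the "average and standard deviation of first 14 days of available data", gathered over two to six weeks. A high-activity day is one more than one SD above the child's mean.

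Section 5a then sets out the analyses:
- "Correlations will be performed to assess if there is relationship between daytime activity (8- am to 9 pm) and nighttime nadir blood glucose level", with nadir taken as continuous. No covariate or restriction of nights is given.
- A binary logistic model for hypoglycemia, "used to assess the significance of daytime activity, insulin dosing, and carbohydrate intake, as independent factors increasing the risk of hypoglycemia", followed by generalized estimating equations. Insulin dosing is not defined.
- Two analysis sets: "The intention to treat analysis will include all data", while "per protocol analysis will exclude cases in which the subject does not comply with recommendations of the study team" or does not finish the 12 weeks.
- A final-week comparison, which begins "In the event usual-care pump settings are adjusted during the course of the study". It is meant to separate the effect of activity data from that of CGM, and does not bear on the activity–nadir association.

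**The concern.** The exposure (daytime activity) triggers a treatment designed to cancel the exposure's effect on the outcome (overnight nadir). Pooling treated and untreated nights without a term for treatment mixes the physiological association with the success of the intervention: the better the reductions work, the weaker the association looks.

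Neither analysis set helps. Intention to treat keeps every night. Per protocol removes cases of non-compliance, so it keeps the nights on which a reduction was followed.

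At stake is the evidence behind the specific aim (section 1), which is to predict when an adjustment is needed. So is the estimate taken forward to the larger study, where prediction of nadir from activity is a secondary outcome (section 4d).

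**Working it through.** The plan states no slope, correlation or power, so there is no figure to reproduce. Direction and size were checked under stated assumptions.

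**Inputs from the plan.** 20 children; 3 to 4 months (taken as 84 or 112 nights); flag at mean + 1 SD; reductions possible after 14 nights, or as late as six weeks (42 nights).

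**Assumed.** Activity z is normal within child; true slope −8 mg/dL per SD; night-to-night SD 28; between-child SD 15; mean nadir 100.

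**Step 1: ceiling, every flagged night fully corrected.**
- P(z > 1) = 0.159, φ(1) = 0.242, mean z on flagged nights = 0.242/0.159 = 1.525.
- Lift that restores the mean nadir on flagged nights: 8 × 1.525 = 12.2 mg/dL.
- Proportional loss of slope = f × φ(1) × 1.525 = f × 0.369, where f is the share of nights after dosing starts.

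| Nights | Dosing after night | f | Loss | Slope |
|---|---|---|---|---|
| 84 | 14 | 0.833 | 31% | −5.5 |
| 84 | 42 | 0.500 | 18% | −6.5 |
| 112 | 14 | 0.875 | 32% | −5.4 |
| 112 | 42 | 0.625 | 23% | −6.2 |

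Simulation with each child's own 14-night threshold gives 19–33%. Within-child r starts at −8/√(8² + 28²) = −0.27 and falls to between −0.19 and −0.22.

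**Step 2: the incremental rule in section 3.** Its example moves a nadir of 50 into the range 110–130 in six changes of 0.05 U/hr. One step is therefore worth (110 − 50)/6 = 10 to (130 − 50)/6 = 13.3 mg/dL. The first change needs a repeat nadir of 50. Against a target of 120, the slower gain has a cumulative-error threshold of 2 × 70 = 140. The fastest gain at which one such nadir does not suffice has a threshold just above 70 (71 used). The derivative term was left out, and error was taken against each child's mean baseline nadir.

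| Scenario | Flagged nights treated | Loss of slope |
|---|---|---|
| Slower gain | 12–37% | 2–14% |
| Fastest gain | 31–52% | 6–23% |
| Full correction after two flagged nadirs below 70 | – | 5–17% |

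**Step 3: limits on direction.** If no reductions are made, or they have no effect, there is no bias. In the 84-night, 14-night-baseline case the sign reverses only beyond about 1/0.308 = 3.2 times full correction.

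**Step 4: logistic/GEE model.** Log odds ratio per SD over 12 weeks:
- untreated: 0.45–0.46;
- reductions made, no term: 0.30–0.36 at the ceiling, 0.37–0.44 under the incremental rule;
- with the reduction term: 0.44–0.46.

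A separate run (assumed slope −10) gave 0.37 with no insulin term, 0.39 with a noisy insulin measure in which the basal cut is a small part, and 0.59 with an exact reduction-night term. An insulin covariate protects only if it captures the reduction.

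**Step 5: which variable to adjust for.** With a term for the study's own reduction, the slope returns to −8.0 to −8.1 in every linear case. Total delivered basal does equally well only if basal does not respond to that night's glucose. Section 4c sets a low alarm at 60 mg/dL and leaves treatment of lows to the home routine. Suppose families make a full-size cut after a low on 25% or 50% of nights with nadir below 60 (assumed). In the delayed-dosing case the delivered-basal term gives −6.3 or −5.2, against −6.9 with no adjustment. Across the dosing patterns tried it gives −3.3 to −6.2, while the study-reduction term stays at −7.9 to −8.1.

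**The case against.** The strongest reply has four parts.

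1. *The plan already has an insulin covariate.* This is true of the logistic model. A reader might infer that no analysis in the plan adjusts for insulin; section 5a does not support that. There the gap is an undefined covariate, while the correlation has no such term at all.

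2. *The effect is small under the protocol's own rule.* At the slower gain the loss is 2–14%, or about 0.2–1.1 mg/dL on a slope of −8, against a standard error near 0.7. That stands. A reader might take the 20–33% range as the expected loss, but it needs every flagged night fully corrected from the start. Section 3 requires repeated lows before a change, and section 4c requires a physician's approval.

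3. *The pilot is unpowered and has no planned hypothesis.* This also stands. Feasibility is judged on whether the data can be assembled and recommendations are accepted, which this bias does not touch. A reader might infer that the larger study's sample size will be inflated. The documents do not say so: its primary endpoint is the incidence of nighttime hypoglycemia. Only if this slope were used for sizing would the effect arise. A 2–14% loss would then multiply the sample size by 1/0.98² = 1.04 to 1/0.86² = 1.35.

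4. *Adjustment can do harm.* This is right for total delivered basal, as step 5 shows. It governs the choice of term but does not defend leaving the correlation unadjusted.

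**Conclusion.** The concern holds for the activity–nadir correlation, and for the logistic/GEE model to the extent that insulin dosing fails to capture the activity-triggered reduction. The bias is toward zero where reductions are made and work as intended. Under the assumed effect sizes the loss is about 2–14% at the slower incremental gain, up to about 23% at the fastest, and roughly 20–33% as a ceiling.

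The direction follows from the protocol's own text. The sizes rest on an assumed slope, SDs, normal activity and dosing pattern, none of which the documents give. A reversed sign would need correction of about three times the full amount. The consequence is an understated association passed to the larger study, not a wrong feasibility conclusion. It should be fixed in the analysis text; it is not a reason to change the design.

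**What to change.** In section 5a:
1. Estimate the activity–nadir association within subject on all nights, with a term for the study's activity-triggered reduction in force that night. Use an indicator, or the programmed size relative to the usual-care setting then in force, fixed before that night's glucose is seen. The current setting matters because usual-care settings may change during the study.
2. Put the same term in the logistic/GEE model, separate from other insulin dosing.
3. Report as a sensitivity analysis the estimate from nights before each child's first activity-based change.
4. Do not use total delivered overnight basal as the main adjustment. Reductions that families make before the night because of activity may be added in a sensitivity analysis only, where the pump record shows they preceded any low.

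The cost is SAP wording and a little analysis: pump histories are downloaded weekly (section 5), and changes are noted in the medical record (section 4c). The downsides are:
- **Precision.** The slope's standard error is about 5% larger under delayed or incremental dosing and about 20% larger at the ceiling (0.86 against 0.71 at 12 weeks).
- **Linearity.** With an assumed threshold-shaped effect (untreated slope −2.9), the adjusted slope is −2.4 to −2.8 under delayed or incremental dosing and −1.5 to −1.6 at the ceiling. Pre-change nights give −2.8 to −2.9 and −2.5 respectively. If the two estimates differ materially, report the adjusted one as dependent on linearity.
- **Residual attenuation.** Section 3 says many subjects find they need to lower basal on such nights. If families do so on 25–50% of high-activity baseline nights (assumed), the 14-night baseline slope is already −7.3 to −6.4, and the study-reduction term does not recover this.
- **Convergence.** In the case with fewest treated nights, 25 of 200 GEE fits with the added term failed. If that happens, report the pre-change estimate.
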